7.1.5 CO MONITORING USING THE CFK EQUATION

Subjects will be administered iCO at 200 ppm or placebo (medical grade air) for up to 90 minutes on each study day for up to 3 consecutive days.

COHb levels will be measured at baseline prior to treatment and after 20 minutes of iCO administration. These two COHb levels will be used to look up the time at which the COHb level is predicted to be 8% using a CFK equation-based table (**Appendix B or electronic equivalent version in StudyTRAX**). If the COHb level is predicted to be 8% prior to 90 minutes, the study drug will be stopped at that time to ensure that subjects do not exceed a COHb level of 10% and safely achieve a target COHb level of 5-8%.

Blood will be drawn for baseline COHb level prior to iCO or placebo administration using the bedside IL GEM Premier Co-oximeter. Arterial or venous blood will be drawn for pre-treatment blood gas analysis performed at the local clinical laboratory.

1. Subjects will be treated with placebo air or iCO at 200 ppm.
2. After 20 minutes, blood will be drawn for COHb measurement using the bedside IL GEM Premier Co-oximeter.
3. The CFK equation-based table will be used to look up the time at which the COHb level is predicted to be 8%.
4. Blood will be drawn for COHb measurements at 60 min, 75 min, 90 min, and 180 min. Blood will also be drawn for blood gas analysis at the local clinical laboratory at 90 min at the completion of the study drug.

On days 1-3, a total of approximately 2.5 mL of blood will be drawn during the study drug administration for safety monitoring of COHb levels and blood gas analysis.

7.1.6 DAILY HOLD PARAMETERS PRIOR TO DRUG ADMINISTRATION

Subjects will be assessed daily prior to study drug administration as described in the **Time-Events Schedule (Section 1.3)**.

Administration of the study drug will be held if the following criteria are met.

- COHb level $\geq 3\%$
- Lactate ≥ 4 mmol/L
- ST elevation MI or unstable angina/non ST elevation MI concerning for ACS
- Unstable atrial or ventricular arrhythmia

Subjects will have blood drawn daily for measurement of COHb and lactate prior to administration of study drug. If COHb $\geq 3\%$ or lactate ≥ 4 mmol/L, the study drug will be held until the next scheduled dose the following day. Lactate and COHb will be measured the following day to determine whether the study drug will be administered. If the study drug is being held for another reason, COHb levels will not be measured on days the study drug is being held.

A 12 lead EKG will also be performed and reviewed daily by the study staff physician prior to study drug administration to evaluate for cardiac exclusion criteria (eg. acute MI, acute coronary syndrome (ACS), or unstable atrial or ventricular arrhythmia). If a subject meets the following criteria for ST elevation MI or unstable angina/non ST elevation MI concerning for ACS according to the American College of Cardiology Foundation/American Heart Association guidelines¹⁴⁷⁻¹⁴⁹, they will be excluded from enrollment or further study drug administration according to exclusion criteria.

ST elevation MI (STEMI) Criteria: New ST elevation at the J point in at least 2 contiguous leads of ≥ 2 mm (0.2 mV) in men or ≥ 1.5 mm (0.15 mV) in women in leads V2–V3 and/or of ≥ 1 mm (0.1 mV) in other contiguous chest leads or the limb leads; New or presumably new left bundle branch block (LBBB)¹⁴⁷⁻¹⁴⁹.

Unstable angina/non ST elevation MI (NSTEMI): Ischemic ST-segment depression ≥ 0.5 mm (0.05 mV) or dynamic T-wave inversion with pain or discomfort; Nonpersistent or transient ST-segment elevation ≥ 0.5 mm for < 20 minutes. Threshold values for ST-segment depression consistent with ischemia are J-point depression 0.05 mV (-0.5 mm) in leads V2 and V3 and -0.1 mV (-1 mm) in all other leads (men and women)¹⁴⁷⁻¹⁴⁹.

Note, troponin (I or T) may be increased in patients with sepsis and ARDS¹⁵⁰ in the absence of an acute MI or ACS from coronary artery disease. If, in the judgment of the clinical team, an ARDS patient with elevated troponin levels has no other indication of an MI or ACS, the patient may still be eligible for enrollment.

In addition, if a subject develops the following criteria during the study, the study drug will be held until resolved:

- Severe hypoxemia defined as $\text{SpO}_2 < 95$ or $\text{PaO}_2 < 90$ on $\text{FiO}_2 \geq 0.9$
- Hemoglobin < 7.0 g/dL
- Diffuse alveolar hemorrhage from vasculitis
- Use of high frequency ventilation
- Use of inhaled pulmonary vasodilator therapy (eg. NO or prostaglandins)
- Use of ECMO

If study drug hold criteria are met, the study drug will be held and subjects will be evaluated on a daily basis and assessed for whether a given criteria has resolved and whether study drug treatment may be resumed.

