1.4 DEFINITIONS

Acute Kidney Injury: Acute kidney injury network Stage 3 disease, defined as a threefold increase in creatinine from baseline or the need for dialysis

Completing 48 hours of UAB (from weaning form): Defined as the date (calendar day) that the subject reaches exactly 48 hours of UAB. Example: if subject meets UAB at 1900 on 6/1/06 and does not return to AB, then the date of completing 48 hours of UAB would be 6/3/06.

Date of first UAB (from Study Termination form): Defined as the first day that the subject is on UAB from midnight to midnight. Example: if subject meets UAB at 1900 on 6/1/06, then the date of first UAB would be 6/2/06, as long as subject does not return to AB on 6/2/06.

Day zero: Defined as day of randomization. Study days are calendar days.

Drug held/hold drug: Study medication withheld for 24 hours.

Drug permanently discontinued: Study medication stopped for remainder of the trial.

Enrollment: The primary analysis population will be the modified intention-to-treat (MITT) population. All randomized subjects treated with at least one dose of the study drug will be included in the analysis. Because some patients may withdraw or have a change in clinical status precluding dosing of study drug (eg. post-randomization lactic acidosis), we may randomize additional patients to achieve the enrollment goal of 32 patients who are randomized and treated with at least one dose of the study drug. We expect this to be an uncommon occurrence. Patients who are randomized but do not undergo any study procedures or study treatment will not be included in the study analysis.

Extubation: Removal of an orotracheal, nasotracheal tube, or unassisted breathing with a tracheostomy.

Home: level of residence or health care facility where the patient was residing prior to hospital admission

Hospital Mortality to Day 60: This primary endpoint includes all deaths following randomization in any health care facility prior to discharge “home” until study day 60. Study subjects still in a health care facility at study day 61 are considered alive for this endpoint.

Interruption of Dosing During Drug Administration: Study medication prematurely stopped prior to 90 minutes.

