6.2 EXCLUSION CRITERIA

An individual who meets any of the following criteria will be excluded from participation in this study:

1. Age less than 18 years
2. Greater than 168 hours since ARDS onset
3. Pregnant or breastfeeding
4. Prisoner
5. Patient, surrogate, or physician not committed to full support (exception: a patient will not be excluded if he/she would receive all supportive care except for attempts at resuscitation from cardiac arrest)
6. No consent/inability to obtain consent or appropriate legal representative not available
7. Physician refusal to allow enrollment in the trial
8. Moribund patient not expected to survive 24 hours
9. No arterial or central line/no intent to place an arterial or central line
10. No intent/unwillingness to follow lung protective ventilation strategy
11. Severe hypoxemia defined as $\text{SpO}_2 < 95$ or $\text{PaO}_2 < 90$ on $\text{FiO}_2 \geq 0.9$
12. Hemoglobin < 7.0 g/dL
13. Subjects who are Jehovah's Witnesses or are otherwise unable or unwilling to receive blood transfusions during hospitalization
14. Acute myocardial infarction (MI) or acute coronary syndrome (ACS) within the last 90 days
15. Coronary artery bypass graft (CABG) surgery within 30 days

16. Angina pectoris or use of nitrates with activities of daily living
17. Cardiopulmonary disease classified as NYHA class IV
18. Stroke (ischemic or hemorrhagic) within the prior 1 month, cardiac arrest requiring CPR within the prior 72 hours, or inability to assess mental status following cardiac arrest
19. Burns > 40% total body surface area (TBSA)
20. Severe airway inhalational injury
21. Use of high frequency oscillatory ventilation
22. Use of extracorporeal membrane oxygenation (ECMO)
23. Concomitant use of inhaled pulmonary vasodilator therapy (eg. nitric oxide [NO] or prostaglandins)
24. Diffuse alveolar hemorrhage from vasculitis
25. Concurrent participation in other investigational drug study

Reasons for Exclusions:

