7.1.8 PERMANENT DISCONTINUATION OF STUDY DRUG ADMINISTRATION

Permanent discontinuation of the study drug is defined as cessation of the study drug without the intent of restarting the study drug during the three-day treatment period.

Permanent discontinuation of the study drug inhalation will occur in the following situations:

- **Occurrence of pre-specified administration related adverse events:**
 - Acute MI within 48 hours of study drug administration
 - Acute CVA within 48 hours of study drug administration
 - New onset atrial or ventricular arrhythmia requiring DC cardioversion within 48 hours of study drug administration
 - Increased oxygenation requirements defined as: an increase in FiO₂ of ≥ 0.2 **AND** increase in PEEP ≥ 5 cm H₂O within 6 hours of study drug administration
 - Increase in any protocol-specified measurement of COHb to ≥ 10%
 - Increase in lactate by ≥ 2 mmol/L within 6 hours of study drug administration
- If the patient experiences serious adverse events ***related to the study drug (Section 9.7)***.
- If the investigator, attending physician, the patient or their surrogate decides that the study drug should be discontinued. If this decision is made because of an AE, then appropriate AE reporting procedures will be followed (**Section 9.7**).
- Daily baseline COHb levels greater than 3% leading to three missed drug doses.
- Three or more missed drug administrations due to AEs.

Subjects who have their study drug permanently discontinued will continue their participation in the study, and will be followed to determine their vital status and perform neurocognitive testing at 6 months, as outlined in the **Time-Events Schedule (Section 1.3)**.

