9.5.1 REVIEW PARAMETERS PRIOR TO ADMINISTRATION OF STUDY DRUG

Review the Daily Hold Parameters (detailed information in **Section 7.1.6**). Administration of the study drug will be held if the following criteria are met.

Daily Hold Parameters:

- COHb level $\geq 3\%$
- Lactate ≥ 4 mmol/L
- ST elevation MI or unstable angina/non ST elevation MI concerning for ACS
- Unstable atrial or ventricular arrhythmia
- Severe hypoxemia defined as SpO₂ < 95 or PaO₂ < 90 on FiO₂ ≥ 0.9
- Hemoglobin < 7.0 g/dL
- Diffuse alveolar hemorrhage from vasculitis
- Use of high frequency ventilation
- Use of inhaled pulmonary vasodilator therapy (eg. NO or prostaglandins)
- Use of ECMO
- Occurrence of an AE meeting criteria for study drug hold or discontinuation (**Sections 7.1.6, 7.1.8.**).

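### Section 7.1.6 attaches both a resumable hold and a bar on further study drug to the same pre-dose EKG finding of STEMI or unstable angina/NSTEMI, and Section 7.1.8 settles only part of the conflict

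*Combined protocol and SAP*

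**What the plan says.** The protocol deals with a coronary finding on the daily pre-dose EKG in several places.

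- **Hold.** Section 7.1.6 lists it among the daily hold parameters, and Section 9.5.1 repeats the item: "ST elevation MI or unstable angina/non ST elevation MI concerning for ACS". The EKG step in Section 9.5 has the tracing reviewed for a possible hold.
- **What a hold means.** Section 1.4 has "Drug held/hold drug: Study medication withheld for 24 hours", set apart from "Drug permanently discontinued: Study medication stopped for remainder of the trial". Section 7.1.6 closes with the procedure that follows: "the study drug will be held and subjects will be evaluated on a daily basis and assessed for whether a given criteria has resolved". Restarting treatment is considered at the same review. Section 8.1 says the same.
- **Bar.** Between its hold list and that closing sentence, 7.1.6 sets out EKG criteria for STEMI and for unstable angina/NSTEMI. It says of subjects who meet them that "they will be excluded from enrollment or further study drug administration according to exclusion criteria". The exclusion in question is criterion 14 of Section 6.2: "Acute myocardial infarction (MI) or acute coronary syndrome (ACS) within the last 90 days".
- **Permanent discontinuation.** The event list in Section 7.1.8 includes "Acute MI within 48 hours of study drug administration". It does not include unstable angina or ACS without infarction.
- **Discretionary or conditional routes.** Section 7.1.8 also stops drug for good on the decision of the investigator or attending physician, or for a drug-related SAE. Section 8.2 allows, but does not require, withdrawal of a participant who newly meets an exclusion criterion.

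**The concern.** One EKG result leads to two instructions in the same section. One withholds today's dose and leaves later doses possible. The other ends dosing. The list that staff work through before each dose carries only the first.

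Three things are at stake.

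- **Patient safety.** Section 6.2 explains that recent MI, recent CABG and angina are excluded because lowering oxygen delivery to the myocardium could add risk. Under the hold text, a patient of that kind could receive a remaining dose.
- **The safety endpoint.** Acute MI within 48 hours of study drug is a component of the primary safety endpoint (4.3, 10.1). A dose given after a hold opens a new 48-hour window, and a barred dose does not. Exposure to that component would then depend on which paragraph a site follows.
- **The analysis set.** Section 10.3 limits the primary population to subjects with at least one dose, and Section 8.2 lets undosed subjects be replaced. A patient with a coronary finding before the first dose could enter the analysis under one reading and drop out of it under the other.

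**Working it through.** The documents give no figure to reproduce here. The check is a comparison of the rules, followed by a count of doses.

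**Step 1: the rules by situation.**

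| Situation | Hold text (7.1.6 list, 9.5.1) | 7.1.6 EKG paragraph | 7.1.8 event list | Settled? |
|---|---|---|---|---|
| A. Acute MI within 48 h after a dose | Hold, reassess daily | No further drug | Permanent discontinuation | Yes, by 7.1.8 |
| B. MI on the EKG before the first dose | Hold, reassess daily | No drug | Not triggered: no dose yet | No |
| C. MI more than 48 h after the last dose | Hold, reassess daily | No further drug | Not triggered: outside window | No |
| D. Unstable angina/ACS without MI | Hold, reassess daily | No further drug | Not listed | No |

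In B, C and D the only other routes are the discretionary or conditional ones in 7.1.8 and 8.2. They permit a stop but do not fix one. Section 7.1.6 also gives a single set of EKG criteria for unstable angina and NSTEMI together. Those criteria alone do not tell a site whether a patient belongs in A or D.

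**Step 2: can the hold lift in time for a later dose?** The only next-day rule that 7.1.6 writes out is for COHb and lactate. For the cardiac item, the 24 hours comes from Section 1.4, and restarting depends on the criterion having resolved. The documents do not say when an MI or ACS counts as resolved. The 7.1.6 criteria include transient ST elevation lasting under 20 minutes, which can be absent from the next day's EKG. Restarting within the course is therefore possible, but it is neither automatic nor certain.

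**Step 3: how many doses differ?** Assume one dose a day on Days 1 to 3, with held doses not made up (7.1.3, 9.5.2). For a pre-dose finding on Day d, the bar allows no more doses and the hold allows at most 3 − d.

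- Day 1: 3 − 1 = 2 doses (B or D).
- Day 2: 3 − 2 = 1 dose (D, or B if Day 1 was held for another reason).
- Day 3: 3 − 3 = 0 doses.

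Situation C needs a gap after the last dose, for example a Day 1 dose, a Day 2 hold and a finding on Day 3 just past 48 hours. On the assumption above, no dose is then left, so the conflict in C is one of wording only. It would affect dosing if treatment could run past Day 3. The completion rule in Section 2, which refers to the third dose, could be read to allow that.

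**The case against.** The strongest reply is that the two texts can be read together: withhold today's dose, and if the stated EKG criteria are met, give no more. A specific sentence ordinarily governs a general one. Section 9.5.1 sends the reader to 7.1.6 for detail and to 7.1.8 for adverse events, and the EKG step in 9.5 is said to look for cardiac exclusion criteria. Section 7.1.8 already stops drug after an MI within 48 hours of a dose, which in daily dosing covers most infarctions once treatment has begun. A physician must also review each EKG before dosing.

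Much of this stands and limits the point. It does not remove it. Reading the sentences together leaves the cardiac item on a list whose stated consequence is daily reassessment for restarting. The cross-reference in 9.5.1 leads back to the section that contradicts itself.

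A reader might infer two stronger claims that the documents do not support.

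- **That the plan lets drug restart 24 hours after any coronary event in a patient whom exclusion 14 bars for 90 days.** The 24 hours is the Section 1.4 definition, restarting is conditional on resolution, and MI soon after a dose is already a permanent stop. Exclusion 14 is an enrolment criterion that reaches dosing only through the 7.1.6 sentence. In a three-day course, setting 24 hours against 90 days adds nothing to the question of whether any remaining dose may be given.
- **That ACS without MI can never end treatment.** The routes in 7.1.8 and 8.2 can end it, but they rest on judgment or on a finding that the event is drug-related.

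**Conclusion.** The contradiction is real and should be resolved, because it concerns whether to dose after a suspected coronary event. It is confined to an MI found before the first dose, an MI more than 48 hours after the last dose, and unstable angina/ACS without MI. Acute MI within 48 hours of a dose is settled by 7.1.8.

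Per patient, the size is up to two 90-minute administrations for a Day 1 finding and one for a Day 2 finding. This assumes a course confined to Days 1 to 3, and a physician who judges the criterion resolved by the next dosing day. How many of the 32 patients this would affect cannot be estimated, since the documents give no event rate. The exclusions for recent MI/ACS, recent CABG, angina and NYHA class IV make it less likely. The effect on the safety comparison therefore remains unquantified, and the case for acting rests on the conflicting instruction itself.

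**What to change.** Reconcile Sections 1.4, 7.1.6, 7.1.8, 8.2, 9.5 and 9.5.1, and the link from 7.1.6 to exclusion 14, so that a STEMI or unstable angina/NSTEMI finding has one stated consequence before the first dose and one between doses.

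- Place the finding under a single heading, either hold or permanent discontinuation, at each of those time points.
- If any form of it stays under hold, state how the general 24-hour definition and the daily reassessment apply to it.
- State whether a newly met exclusion criterion governs dosing after enrolment, and align the discretionary wording in 8.2 with the answer.
- Make the pre-treatment checklist named in 9.5 match.

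Which rule stands is for the sponsor's clinicians to decide. The cost is protocol wording in these sections and one checklist revision, with no new assessments and no change to sample size.

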7.1.7 INTERRUPTION OF DOSING DURING STUDY DRUG ADMINISTRATION

Subjects will have blood drawn for measurement of COHb levels prior to study drug treatment and 20 min, 60 min, 75 min, 90 min, and 180 min after the start of study drug treatment. It is anticipated that the predicted and measured COHb levels will not exceed the COHb target range of 5-8% given the impaired diffusion capacity

in ARDS patients. However, the following parameters will be used to shorten the 90 minute treatment duration should CO uptake be higher than anticipated:

The study drug will be stopped prior to 90 minutes:

1. If the measured COHb level is > 8% at any time during study drug treatment.
2. If the COHb level is predicted to be 8% prior to 90 minutes according to the CFK equation-based table. If this occurs, study drug treatment will be stopped at the time the COHb level is predicted to be 8% by the CFK equation-based table and blood COHb level will be measured at that time.
3. If the investigator, attending physician, the patient, or their surrogate decides that the study drug should be discontinued.

If COHb levels unexpectedly exceed our target level, in addition to discontinuation of the study drug, subjects will be placed on 100% O₂ to accelerate CO elimination until COHb levels normalize.

7.1.8 PERMANENT DISCONTINUATION OF STUDY DRUG ADMINISTRATION

Permanent discontinuation of the study drug is defined as cessation of the study drug without the intent of restarting the study drug during the three-day treatment period.

Permanent discontinuation of the study drug inhalation will occur in the following situations:

- **Occurrence of pre-specified administration related adverse events:**
 - Acute MI within 48 hours of study drug administration
 - Acute CVA within 48 hours of study drug administration
 - New onset atrial or ventricular arrhythmia requiring DC cardioversion within 48 hours of study drug administration
 - Increased oxygenation requirements defined as: an increase in FiO₂ of ≥ 0.2 **AND** increase in PEEP ≥ 5 cm H₂O within 6 hours of study drug administration
 - Increase in any protocol-specified measurement of COHb to ≥ 10%
 - Increase in lactate by ≥ 2 mmol/L within 6 hours of study drug administration
- If the patient experiences serious adverse events ***related to the study drug (Section 9.7)***.
- If the investigator, attending physician, the patient or their surrogate decides that the study drug should be discontinued. If this decision is made because of an AE, then appropriate AE reporting procedures will be followed (**Section 9.7**).
- Daily baseline COHb levels greater than 3% leading to three missed drug doses.
- Three or more missed drug administrations due to AEs.

Subjects who have their study drug permanently discontinued will continue their participation in the study, and will be followed to determine their vital status and perform neurocognitive testing at 6 months, as outlined in the **Time-Events Schedule (Section 1.3)**.

7.1.9 COMPLETION OF THE STUDY DRUG ADMINISTRATION

Subjects will be considered to have completed the study drug administration portion of the study when one of the following conditions is met, whichever comes first:

1. Three days after study drug administration
2. Discontinuation of mechanical ventilation
3. Death

